10.4.1.1. Events Meeting the AE Definition

- Any abnormal laboratory test results (hematology, clinical chemistry, or urinalysis) or other safety assessments (eg, ECG, radiological scans, vital signs measurements), including those that worsen from baseline, considered clinically significant in the medical and scientific judgment of the investigator (ie, not related to progression of underlying disease).
- Exacerbation of a chronic or intermittent pre-existing condition including either an increase in frequency and/or intensity of the condition.
- New conditions detected or diagnosed after study intervention administration even though it may have been present before the start of the study.
- Signs, symptoms, or the clinical sequelae of a suspected drug-drug interaction.
- Signs, symptoms, or the clinical sequelae of a suspected overdose of either study intervention or a concomitant medication.

10.4.1.2. Events NOT Meeting the AE Definition

- Any clinically significant abnormal laboratory findings or other abnormal safety assessments which are associated with the underlying disease, unless judged by the investigator to be more severe than expected for the subject's condition.
- The disease/disorder being studied or expected progression, signs, or symptoms of the disease/disorder being studied, unless more severe than expected for the subject's condition.
- Medical or surgical procedure (eg, endoscopy, appendectomy): the condition that leads to the procedure is the AE.
- Situations in which an untoward medical occurrence did not occur (social and/or convenience admission to a hospital).

10.4.2. Serious Adverse Event

An SAE is any untoward medical occurrence that at any dose:

- Results in death.
- Is life-threatening.
 - The term “life-threatening” in the definition of “serious” refers to an event in which the subject was at risk of death at the time of the event. It does not refer to an event, which hypothetically might have caused death, if it were more severe.
- Requires inpatient hospitalization or prolongation of existing hospitalization.
 - In general, hospitalization signifies that the subject has been detained (usually involving at least an overnight stay) at the hospital or emergency ward for observation and/or treatment that would not have been appropriate in the physician’s office or outpatient setting. Complications that occur during hospitalization are AEs. If a complication prolongs hospitalization or fulfills any other serious criteria, the event is serious. When in doubt as to whether “hospitalization” occurred or was necessary, the AE should be considered serious.
 - Hospitalization for elective treatment of a pre-existing condition that did not worsen from baseline is not considered an AE.
- Results in persistent or significant disability/incapacity.
 - The term disability means a substantial disruption of a person’s ability to conduct normal life functions.
 - This definition is not intended to include experiences of relatively minor medical significance such as uncomplicated headache, nausea, vomiting, diarrhea, influenza, and accidental trauma (eg, sprained ankle) which may interfere with or prevent everyday life functions but do not constitute a substantial disruption.
- Is a congenital anomaly/birth defect.
- Is an important medical event.
- Medical or scientific judgment should be exercised in deciding whether SAE reporting is appropriate in other situations such as important medical events that may not be immediately life-threatening or result in death or hospitalization but may jeopardize the subject or may require medical or surgical intervention to prevent one of the other outcomes listed in the above definition. These events should usually be considered serious.
 - Examples of such events include invasive or malignant cancers, intensive treatment in an emergency room or at home for allergic bronchospasm, blood dyscrasias or convulsions that do not result in hospitalization, or development of drug dependency or drug abuse.

10.4.3. Difference between Severity and Seriousness

The term “severe” is often used to describe the intensity (severity) of a specific event (as in mild, moderate, or severe myocardial infarction); the event itself, however, may be of relatively minor medical significance (such as severe headache). This is not the same as “serious,” which is based on subject/event outcome or action criteria usually associated with events that pose a threat to a subject’s life or functioning. Seriousness (not severity) serves as a guide for defining regulatory reporting obligations.

10.4.4. Intensity of Adverse Events

The definition used to assess the intensity of AEs:

Mild: Awareness of sign or symptom, but easily tolerated, ie, does not interfere with subject’s usual function.

Moderate: Discomfort enough to cause interference with usual activity.

Severe: Incapacitating with inability to work or do usual activity, ie, interferes significantly with subject’s usual function.

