8.8.1. Adverse Events

8.8.1.1. Methods to Detect Adverse Events

The definitions of an AE or SAE can be found in Section 10.4. AEs may be directly observed, reported spontaneously by the subject or by questioning the subject (or, when appropriate, by a caregiver, surrogate, or the subject's legally authorized representative) at each study visit. Subjects should be questioned in a general way, without asking about the occurrence of any specific symptoms. The investigator must assess all AEs to determine seriousness, severity, and causality. The investigator and any qualified designees are responsible for detecting, documenting, and recording events that meet the definition of an AE or SAE and remain responsible for following AEs that are serious, considered related to the study drug or study procedures, or that caused the subject to discontinue.

All clinical laboratory results, vital signs, and ECG results or findings should be appraised by the investigator to determine their clinical significance. Isolated abnormal laboratory results, vital sign findings, or ECG findings (ie, not part of a reported diagnosis) should be reported as AEs if they are symptomatic, lead to study drug discontinuation, require corrective treatment, or constitute an AE in the investigator's clinical judgment.

Medical conditions (including laboratory values/vital signs that are out of range) that were diagnosed or known to exist prior to informed consent will be recorded as part of medical history. COVID-19 assessments are detailed in Section 8.8.2.

8.8.1.2. Time Period for Collecting Adverse Events, including Adverse Events of Special Interest and Serious Adverse Events

For all randomized subjects, all AEs occurring after the subject signs the ICF and through the EOS Visit, whether observed by the investigator or reported by the subject, will be recorded as detailed in Section 10.1.6.2. All SAEs will be followed until resolution, stabilization, the event is otherwise explained, or the subject is lost to follow-up.

Medical conditions (including clinically significant laboratory values/vital signs that are out of range) that were diagnosed or known to exist prior to the consent date will be recorded as medical history, and not an AE. Exacerbation of a pre-existing medical condition or symptom, including increase in severity of the symptom will be recorded as an AE.

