8.8.3. Clinical Laboratory Evaluations

Blood and urine will be collected for clinical chemistry, hematology, and coagulation tests and for urinalysis at Screening, Day 1, and at subsequent visits as detailed in the SoE ([Table 1.1](#)). Blood for virology will be collected at Screening. Urine tests for drugs of abuse, cotinine, and alcohol will be conducted at Screening.

A nasal (or pharyngeal or oral) swab for COVID-19 testing will be obtained at Screening and on Days 1, 29, and 57.

Refer to Section [10.3](#) for the complete list of laboratory parameters.

Abnormal laboratory values occurring during the clinical study will be followed until repeat test results return to normal (or baseline), stabilize, or are no longer clinically significant. New or worsened clinically significant laboratory abnormalities should be recorded as AEs.

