9.5.2. Safety Data Analyses

All safety analyses will be based on the Safety Analysis Set. All AEs will be coded using the Medical Dictionary for Regulatory Activities (MedDRA). Incidence summary of participants with TEAEs will be presented by maximum severity, SAEs, AESIs, AEs assessed as related to study drug, and AEs resulting in discontinuation of study drug. Observations at each visit and changes from baseline in vital sign recordings, results of laboratory analyses, ECG findings, Ig (IgM, IgG, IgA) values, vaccine (diphtheria, tetanus, and pneumococcus) titers, and lymphocyte subset (CD3-, CD4-, CD8-, CD20-, CD16-, CD56-positive) values will be numerically summarized by treatment group over time. Physical examination findings at each evaluation will be listed.

Listings of all safety endpoints will be generated.

Any medication (other than study drugs) taken by subjects during the course of the study will be recorded and coded using the World Health Organization (WHO) drug dictionary.

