9.5.2.1. Treatment-Emergent Adverse Events

TEAEs are defined as new AEs that occur after the first dose of study drug or as AEs that were present prior to the dose of study drug but which worsened in severity after the start of study drug. An AE will be assigned to the study day in which it started, even if it resolved on a subsequent day. The incidence of TEAEs will be summarized by treatment group.

TEAEs will be further summarized by intensity (Section 10.4.4) and relationship to study drug (Section 10.4.5). Similarly, the number and percentage of subjects reporting treatment-emergent SAEs and related treatment-emergent SAEs will be tabulated, and TEAEs leading to discontinuation of study drug will be tabulated.

A by-subject AE (including treatment-emergent) data listing including but not limited to verbatim term, preferred term (PT), system organ class (SOC), intensity, and relationship to study drug will be provided. Deaths, SAEs, and AEs associated with study drug discontinuation will be listed.

AEs due to COVID-19 will be also summarized and listed.

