10.4. Appendix 4: General Information – Adverse Events

10.4.1. Definition of Adverse Event

An AE is any untoward medical occurrence in a subject administered a pharmaceutical product and that does not necessarily have to have a causal relationship with this treatment. An AE can therefore be any unfavorable and unintended sign (including an abnormal laboratory finding, for example), symptom, or disease temporally associated with the use of a medicinal product, whether or not considered related to the medicinal product.

It is the responsibility of investigators, based on their knowledge and experience, to determine those circumstances or abnormal laboratory findings which should be considered AEs.

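### AE intensity is graded only by symptoms and function, so the severity tables cannot separate large from trivial asymptomatic laboratory AEs, and no laboratory table counts subjects with marked abnormalities

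*Combined protocol and SAP*

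**What the plan says.** **The scale.** Section 10.4.4 defines three intensity grades. Mild begins "Awareness of sign or symptom, but easily tolerated, ie, does not interfere with" usual function. Moderate is "Discomfort enough to cause interference with usual activity". Severe begins "Incapacitating with inability to work or do usual activity, ie, interferes significantly with" usual function. None refers to the size of a laboratory value, and no other intensity scale appears in the text.

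**Laboratory findings as AEs.** Section 10.4.1 says an AE can be "any unfavorable and unintended sign (including an abnormal laboratory finding, for example), symptom, or disease temporally associated" with the product. Section 8.8.1.1 says that isolated abnormal results "should be reported as AEs if they are symptomatic, lead to study drug discontinuation, require corrective treatment, or constitute an AE" in the investigator's judgment. Section 8.8.3 adds: "New or worsened clinically significant laboratory abnormalities should be recorded as AEs". Section 8.8.1.3 requires a severity assessment for every AE.

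**The analysis.** Section 9.5.2 states: "Incidence summary of participants with TEAEs will be presented by maximum severity". Section 9.5.2.1 also summarizes treatment-emergent AEs (TEAEs) by intensity and refers to Section 10.4.4 by number. Its TEAE definition has two limbs: new AEs after the first dose, and "AEs that were present prior to the dose of study drug but which worsened in severity after the start of study drug". For laboratory results, Section 9.5.2.4 plans descriptive statistics, change from baseline, and mean change for the maximum, minimum and last values.

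**The concern.** Safety is the primary objective, and laboratory results are among the named primary endpoints (Table 3.1). A reader of the severity table will take an empty Moderate or Severe row to mean that no marked event occurred. For asymptomatic laboratory AEs that inference fails, because the scale asks what the subject felt or could not do, not how abnormal the value was. If investigators depart from the written definitions and use their own judgment, the grade has no common standard across roughly 20 to 30 sites enrolling up to 24 subjects. Either way, the severity label carries little information for this class of event. The study is meant to inform a go/no-go decision (Section 2.2), so the safety tables should show how many subjects had a marked abnormality.

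**Working it through.** The documents state no figure on this point and the study has no power calculation (Sections 9.1 and 9.2), so there is nothing to reproduce. The check is mainly a literal reading.

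**1. Can an asymptomatic laboratory finding be an AE?** Yes. The Section 8.8.1.1 criteria are joined by an or, and being symptomatic is only one of them. Section 8.8.3 turns on clinical significance, not symptoms.

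**2. What grade does it receive?** Three invented records, all without symptoms:

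| Record | Section 10.4.4 grade |
|---|---|
| A. ALT 8 x ULN, new on Day 57 | Mild |
| B. Very low neutrophil count, new after dosing | Mild |
| C. ALT 3.5 x ULN logged as an AE in screening, 9 x ULN after dosing | Mild, then Mild |

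Moderate and Severe both need an effect on activity, which is absent by construction.

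**3. Does it count as a TEAE?** A and B do. The first limb of Section 9.5.2.1 has no intensity condition, so both enter overall incidence and the maximum-severity table, in the Mild row. C depends on record handling:
- If the worsening is a new AE record (Sections 8.8.3 and 10.4.1.1 can be read that way), it starts after the first dose and qualifies under the first limb.
- If it updates the existing record, Mild to Mild has not worsened in severity and fails the second limb.

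The documents do not say which applies.

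**4. Does another summary count affected subjects?** Section 9.5.2.4 gives means and changes. Suppose one of 16 subjects rises by 7 x ULN and the others do not change. The arm mean moves by 7/16 = 0.44 x ULN. A visit maximum, if reported, would show the value but not the number of subjects affected or where they started. By contrast, Section 9.5.2.3 plans the number and percentage of subjects in QTc bands.

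**5. Illustrative size.** Full enrollment of 24 at 2:1 gives 24 x 2/3 = 16 on DS-7011a and 24 x 1/3 = 8 on placebo. One affected active subject is 1/16 = 6.3%, shown as 0/16 = 0% moderate or severe. For an assumed true rate p of marked asymptomatic laboratory AEs, the chance of at least one in n subjects is 1 - (1 - p)^n:

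| Assumed p | n = 16: chance (expected number) | n = 8: chance (expected number) |
|---|---|---|
| 5% | 56% (0.8) | 34% (0.4) |
| 10% | 81% (1.6) | 57% (0.8) |
| 20% | 97% (3.2) | 83% (1.6) |

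No value of p comes from the documents.

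**The case against.** A reader might infer that the TEAE counts miss laboratory toxicity altogether. They do not: a new post-dose laboratory AE is a TEAE at any intensity, and only its row label is affected. A reader might also infer that a worsening pre-dose laboratory AE always drops out of the count. The text does not establish that, since a worsened abnormality may be recorded as its own AE. The situation is also narrow, because it needs a laboratory AE already logged in screening in a subject who is still randomized.

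Several routes do not depend on intensity. Section 10.4.2 names blood dyscrasias among examples of important medical events usually treated as serious, so Record B could appear in the SAE table. TEAEs leading to discontinuation are tabulated. Combined aminotransferase and bilirubin elevations are reported separately (Section 8.8.1.7). All safety endpoints are listed, and with at most 24 subjects listings are a practical review tool. Section 10.4.3 makes seriousness, not severity, the guide for reporting duties. Section 9.5 promises a SAP that could add laboratory grades. Finally, the documents report little toxicity so far: none in monkeys, and one mild, unrelated AE at 20 mg/kg in the preliminary Phase 1a analysis (Sections 2.1 and 2.4).

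Most of this stands and limits the point. It does not remove it. An isolated ALT rise without raised bilirubin, not serious and not leading to discontinuation, reaches none of the special tables. Listings do not give a count by arm. A SAP could supply the missing table, but the text reviewed contains no such provision, and a SAP table alone would not change how investigators assign intensity.

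**Conclusion.** The point holds in a limited form. As written, an asymptomatic laboratory AE of any size is Mild, so the severity and intensity tables cannot grade laboratory toxicity, and no planned laboratory summary counts subjects with marked abnormalities. The possible loss of a worsening pre-dose laboratory AE from the TEAE count is an ambiguity to close, not a demonstrated error.

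The size cannot be derived from the documents. The 6.3% and the probabilities above are illustrations that rest on full enrollment of 24, on assumed rates, and on investigators applying Section 10.4.4 literally. The conclusion also assumes that no separate SAP already specifies laboratory grading. This is a cheap improvement to a primary safety output, not a flaw that invalidates the safety analysis.

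**What to change.** - **Section 9.5.2.4 (or the SAP before database lock):** add a table by treatment group of baseline grade against worst post-baseline grade for each relevant analyte, with the number and percentage of subjects at each grade. Program it from the central laboratory values using a pre-specified numeric scale. CTCAE is one example; the documents name no scale, so the choice is the sponsor's.
- **Section 9.5.2.1:** state that a laboratory AE present before dosing counts as treatment-emergent if its numeric grade rises after the first dose, whether it is entered as a new record or an update.
- **Section 10.4.4:** state that the symptom-based intensity of a laboratory AE is to be read alongside its numeric grade. The investigator's intensity field need not be redefined.

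**Cost.** One more programmed table and some linking of laboratory AE records to their analytes. No new samples or visits are needed: chemistry and hematology are already measured centrally at Screening and on Days 1, 29, 57, 85 and 113 (Table 1.1). Some abnormalities will look more marked than under the present scale. Some subjects will carry a grade at baseline because of their lupus, which is why the table should show the shift from baseline and not the worst value alone.

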10.4.5. Causality Assessment

The investigator should assess causal relationship between an AE and the study drug based on his/her clinical judgment and the following definitions. The causality assessment must be made based on the available information and can be updated as new information becomes available.

- Related:
 - The AE follows a reasonable temporal sequence from study drug administration and cannot be reasonably explained by the subject’s clinical state or other factors (eg, disease under study, concurrent diseases, and concomitant medications).
- Or
- The AE follows a reasonable temporal sequence from study drug administration and is a known reaction to the drug under study (or its chemical group) or is predicted by known pharmacology.
- Not Related:
 - The AE does not follow a reasonable sequence from study drug administration or can be reasonably explained by the subject’s clinical state or other factors (eg, disease under study, concurrent diseases, and concomitant medications).

10.4.6. Action Taken Regarding Study Drug

- Study Drug Not Given: The AE occurred before study drug administration.
- Dose Not Changed: No change in study drug dosage was made.
- Drug Withdrawn: The study drug was permanently stopped.
- Dose Reduced: The dosage of study drug was reduced.

- Drug Interrupted: The study drug was temporarily stopped.
- Dose Increased: The dosage of study drug was increased.
- Not Applicable: Subject died, study treatment had been completed prior to reaction/event, or reaction/event occurred prior to start of treatment.

10.4.7. Other Action Taken for Event

- None.
 - No treatment is required.
- Medication is required.
 - Prescription and/or over-the-counter medication is required to treat the AE.
- Hospitalization or prolongation of hospitalization is required.
 - Hospitalization is required or prolonged because of the AE, whether or not medication is required.
- Other.

10.4.8. Adverse Event Outcome

- Recovered/Resolved
 - The subject fully recovered from the AE with no sequelae observed.
- Recovered/Resolved with Sequelae
 - The subject fully recovered from the AE but with sequelae.
- Recovering/Resolving
 - The AE is improving but not recovered.
- Not Recovered/Not Resolved
 - The AE continues without improving.
- Fatal
 - Fatal should be used when death is a direct outcome of the AE.
- Unknown

10.5. Appendix 5: Allowable Time Windows for Vital Signs, ECGs, and PK/PD Blood Draws

Table 10.2: Allowable Time Windows for Vital Signs, ECGs, and PK/PD Blood Draws

Vital Signs/ECG Procedures (in order of collection)	Allowable Time Window	
	Screening and Day 1	Day 1 and up to Follow-up Visit/End of Study Visit
Vital signs relative to drug administration should be taken:	No more than 5 minutes before the blood collection for safety measurements (inclusive of at least 5 minutes of supine rest with 5 additional minutes allowed).	Vital signs should be taken no more than 10 minutes before PK/PD blood draws (inclusive of at least 5 minutes of supine rest with 1 additional minute allowed). The time between the completion of vital signs and the blood draw may be expanded to 20 minutes when an ECG is scheduled to precede the PK/PD blood draw.
Triplicate 12-lead ECGs should be taken:	No more than 15 minutes before the blood collection for safety measurements (inclusive of at least 5 minutes of quiet rest in the supine position). Allow approximately 2 minutes between triplicate ECGs with 1 additional minute allowed between each of the triplicate ECGs.	When a PK/PD blood collection is scheduled concomitantly with an ECG, then ECG should be taken no more than 15 minutes before the PK/PD blood draws (inclusive of the at least 5 minutes of supine rest with 1 additional minute allowed).
PK/PD Procedures (in order of collection)		Allowable Time Window
PK/PD blood samples		
Days 1, 29, and 57: predose		15 minutes
Day 2 (24 hours after treatment administration)		±60 minutes
Day 8 (1 week after treatment administration)		±1 day
Days 1, 29, and 57: end of infusion		+5 minutes
Days 85, 113, and 169		±3 days
TLR7 and IFN-Type I drawn predose on Day 1 with PD blood sample, on Days 2, 8, 29, 57, 85, and 113		Not applicable

